2.3 Exploratory Objectives

- To evaluate the effect of Cat-PAD on changes in asthma control in asthmatic subjects for up to five years after the administration of treatment.
- To evaluate the effect of Cat-PAD on changes in sleep quality in adults using the Pittsburgh Sleep Quality Index (PSQI) for up to five years after the administration of treatment.
- To evaluate the effect of Cat-PAD on changes in productivity using the Work Productivity and Activity Impairment Questionnaire (WPAI:CIQ-AS) for up to five years after the administration of treatment.

- To evaluate the effect of Cat-PAD on symptomatology on unplanned exposure to a cat in normal daily life in subjects who no longer keep a cat for up to five years after the administration of treatment.
- To evaluate the effect of Cat-PAD on health economic outcomes for up to five years after the administration of treatment.

3.0 STUDY DESIGN

3.1 Overall Study Design

An optional prospective, follow-on study to a randomised, double-blind, superiority, multiple dose, placebo-controlled, parallel group, multi-centre, field study (CP007).

Subjects from participating sites who complete the final Post Administration Collection Period (PAC3) in CP007 will be invited to participate in CP007A. Where possible the Enrolment Visit will occur at the same time as the final Follow-Up Visit as scheduled in CP007. Subjects who consent to take part in this study and who meet all inclusion/exclusion criteria will be issued with paper diary binders and a digital pen (ePRO) to record the required patient reported outcomes data. This comprises annual and monthly evaluations. The annual assessment data will be recorded at the same time of year as the Baseline Allergy Evaluation Period (Visit 2A to Visit 2B) established in CP007. It will include scoring rhinoconjunctivitis symptoms and allergy medication use over a 3-week period, as well as single assessments of quality of life, sleep quality, asthma status and work/school interference. As with CP007, for this study, subjects will receive an Allergy Medication Kit containing approved allergy treatments prior to the start of this 3-week period. The kit will contain the same treatments provided to subjects in CP007.

Additionally, on a monthly basis, subjects will record information in their diary using the digital pen regarding hospital/doctor visits; concomitant medication use; illnesses/symptoms; asthma progression and changes in home environment. Subjects will be requested to upload data from the digital pen monthly via their home computer (internet) directly to a secure website or via a mobile 'phone; if a subject does not have access to a computer, a mobile 'phone will be provided to the subject for the duration of the study and for the sole purpose of uploading data and participating in the study.

Subjects will have up to four visits each year, two of which may be conducted by telephone. At each visit, site staff will record any adverse events (AEs) and serious adverse events (SAEs), and at the on-site visits subjects will be provided with their next diary binder. One of the on-site visits will be scheduled just prior to the annual 3-week symptom and allergy medication use recording period. At this visit, subjects will be provided with an Allergy Medication Kit. For all on-site visits, where possible subjects will be instructed to complete the closest monthly assessment in the diary binder during the visit. Subjects will not be required to undergo any specific treatment or lab tests at these visits.

Subjects will have a final End of Study Visit, which will coincide with the end of the final annual Allergy Evaluation Period assessment.

The duration of this follow-up study will be up to 4 years for each subject.

3.2 Endpoint

3.2.1 Primary Endpoint

- Mean Combined Score (CS) consisting of (TRSS/8 + Allergy Medication Score [AMS]).

The total rhinoconjunctivitis symptom score (TRSS) is the sum of the eight individual symptoms, each of which is scored from 0 to 3 resulting in a range of scores from 0-24. TRSS will be divided by the number of symptoms (8) to provide an average score range of 0-3.

Allergy medications will be provided to subjects to be used according to a pre-specified Allergy Medication Plan (See Appendix 1). Subjects will be requested to use antihistamine eye drops as first line allergy medication for troublesome ocular symptoms; with oral antihistamines and/or intranasal corticosteroids to be added or substituted if subjects have unacceptable nasal symptoms or ocular antihistamines do not provide adequate symptom relief. Oral corticosteroids may be prescribed at the Investigator's discretion. The use of allergy medications will be scored based on Didier (Didier *et al*, 2009) as follows:

- AMS = 0; no allergy medication used per day
- AMS = 0.5; at least one dose of antihistamine eye drops used per day
- AMS = 1; at least one dose of oral antihistamine used per day
- AMS = 2; at least one dose of intranasal corticosteroid used per day
- AMS = 3; at least one dose of systemic corticosteroid used per day

The AMS score is not additive, and therefore the maximum AMS is 3. The TRSS (0-24) and the AMS (0-3) will be combined for analysis of the primary endpoint as follows:

$$CS = TRSS/8 + AMS$$

3.2.2 Secondary Endpoints

- Mean TRSS
- Mean component scores of the TRSS (nasal and ocular)
- Mean AMS
- Mean RQLQ Score

- Concomitant medications associated with rhinoconjunctivitis or related conditions
- AEs

3.2.3 Exploratory Endpoints

- PSQI (if at least 18 years old at time of assessment period)
- 6-Question Asthma Control Questionnaire (ACQ) (excluding lung function) – for asthmatics only
- WPAI:CIQ-AS
- Global assessment of symptom severity on unplanned exposure to a cat in normal daily life in subjects who no longer keep a cat
- Health economic outcomes
- Hospital / Physician office visits
- Asthma progression

4.0 STUDY POPULATION

Only subjects completing the CP007 study will be allowed to enter this follow-up study. No other subjects will be enrolled in the study.

4.1 Number of Subjects

The population is limited to those in the CP007 study and the maximum number to be enrolled in this study will be 1400 subjects. Subjects in countries where fewer than 10 subjects were randomised in CP007 will not be invited to participate in this study.

4.2 Inclusion Criteria

1. Previously randomised into the clinical study CP007 and completed PAC3.
2. Provide written informed consent or assent, as appropriate. (For subjects less than 18 years a Parent/Guardian will also be required to provide written informed consent).
3. Willing and able to comply with the study requirements.

4.3 Exclusion Criteria

1. Started allergen immunotherapy since completing CP007.
2. Has been informed of the treatment received in study CP007.
3. Dependent on the Investigator/site either for employment or education or are first degree relatives or partners of the Investigator/study staff.
4. Subjects institutionalised due to a legal or regulatory order.

4.4 Females of Childbearing Potential

Females of Childbearing Potential (FOCBP) may participate in CP007A without taking any additional precautions to prevent pregnancy as there is no investigational product administration in this study.

4.5 Withdrawal of Subjects from the Study

Subjects will be informed that they have the right to withdraw from the study on their own accord at any time, for any reason and without having to state their reason and that this will not affect their future management and treatment.

4.6 Criteria for Stopping the Study

Circassia Ltd may terminate the study for safety or administrative reasons.

4.7 End of the Study

The end of the study is when the last subject completes the end of study visit (following the last four year annual follow-up assessment).

5.0 STUDY MEDICATION

5.1 Investigational Product

No investigational product will be used in this follow-on study.

Subjects will have received one of the following three study drug regimens in study CP007:

- Single course of Cat-PAD (4 doses of Cat-PAD 6 nmol, 4 weeks apart, followed by 4 doses of placebo, 4 weeks apart)
- Two courses of Cat-PAD (8 doses of Cat-PAD 6 nmol, 4 weeks apart)
- Placebo (8 doses, 4 weeks apart)

5.2 Concomitant Medication and Dietary Supplements

5.2.1 Allergy Medication

In order to ensure consistency with results obtained from CP007, subjects will receive an Allergy Medication Kit prior to the start of the Allergy Evaluation Period to be used as needed. The Allergy Medication Kit will contain the same standardised therapies as those provided in CP007. Subjects will be asked to use only allergy medications provided in the Allergy Medication Kit according to the defined Allergy Medication Plan (Appendix 1) during the Allergy Evaluation period.

5.2.2 Treatment of Suspected Anaphylactic Reactions

Not applicable – subjects will not be deliberately exposed to additional allergen during the study beyond their normal daily exposure from e.g. living with a cat.

5.2.3 Other Medication

Subjects should record the use of all concomitant medications, both prescribed and over-the-counter, into the diary. This includes medications used on both a chronic and an as-needed basis. Hormonal contraceptives may be used by FOCBP.

5.3 Blinding

The subject will not know which treatment they received in CP007 and subjects will waive the right to be told their treatment in CP007 when they enrol in CP007A. If subjects wish to know the treatment they received in CP007 they will be withdrawn from study CP007A. New sequential subject numbers will be assigned to each subject from CP007 as they are enrolled in this study, this reassignment will occur within the electronic data capture (EDC) system to

ensure that all Circassia staff and Quintiles clinical staff directly involved in conduct of the study remain blind to the treatment received in CP007. The CP007 screening and randomisation numbers will not be presented in the CP007A documentation that is available to those who may introduce bias. In order to maintain blinding, once the CP007 study has been unblinded, Investigators and site staff will be kept blinded for any CP007 subjects that have enrolled into CP007A.

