6.2 Study Procedures

6.2.1 Enrolment

Enrolment in to the study may occur at any time after a subject has completed study CP007, but ideally will take place at the final follow-up visit for CP007. Consent may also be taken at the final PAC3 visit (Visit 4F) in CP007.

Subjects will be provided with information about this follow-on study, both verbally and in writing, and written informed consent/assent will be obtained from the subject. Subjects will be provided with a study information sheet to explain the study objectives, as well as any potential risks and benefits. The subject will be given adequate time to read the information sheet and to ask the Investigator any questions. The Investigator must be satisfied that the subject has understood the information provided before written consent/assent is obtained. If there is any doubt as to whether the subject has understood the written and verbal information, the subject should not enter the study.

Subjects agreeing to participate will be asked to sign and date an Informed Consent Form (ICF) or an Informed Assent Form (IAF). For adolescents, informed consent will be obtained from the legally-authorized representatives (e.g. parents/guardians) and informed assent will be obtained from the subject themselves. Any adolescent subjects who turn 18 years of age while in the follow-up portion of this study will be asked to sign a new informed consent form at the next on-site visit, which will include details of an additional questionnaire (PSQI) to be completed on an annual basis. The original signed ICF(s) and IAF(s) will be kept in the subject's medical file and a copy of the signed ICF(s)/IAF(s) will be given to the subject.

Once eligibility for the study is confirmed, subjects will be provided with their study materials, including the subject diary (to include three months of follow-up), digital pen, and if required, mobile telephone to support uploading of data. Site staff will provide training to subjects on how to use the digital pen and completion of the subject diary.

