Adverse events will be recorded as they are reported, whether spontaneously volunteered by a subject or in response to questioning about well-being at each study visit. The subject will be questioned in a general way and no specific symptoms will be suggested. The questioning about AEs will cover the current visit and the period of time between the previous and current visit although subjects may report AEs occurring at any other time during the study. Follow up of all AEs will continue until the overall clinical outcome is definitive. If any AEs have occurred, they will be recorded in the subject's medical record and transcribed to the CRF. The Investigator must detail in the subject records the symptom of the event, the onset of the event, the measures taken and the outcome, the date of disappearance or stabilisation. If known, the diagnosis should be recorded, in addition to the listing of individual signs and symptoms. The Investigator will assess each AE in terms of severity and relationship to study medication as indicated in the sections that follow.

Severity

Mild	Noticeable to the subject, but does not interfere with their usual activities. Usually does not require additional therapy.
Moderate	Interferes with usual activities, possibly requires additional therapy.
Severe	Incapacitating with inability to perform usual activities. May require medical intervention and treatment.

The Investigator will make a judgement regarding whether or not the AE was related to the study medication given in study CP007. However, even if the Investigator feels there is no relationship to the study medication, the AEs **MUST** still be recorded in the CRF and the rationale for the judgement should be recorded in the medical notes.

Causality

Related	Any event that follows a reasonable temporal sequence from administration of study medication given in CP007 OR that follows a known response pattern to the investigational drug. (Any event that does not meet the criteria for unlikely or not related should be classified as related).
Unlikely to be related	Any event that does not follow a reasonable temporal sequence from administration of study medication given in CP007 AND does not follow a known response pattern to the suspected drug.
Not related	Any event that starts before administration of study medication AND/OR for which there is a clear alternative explanation.

Outcome

For each event, the following outcomes are possible:

- Recovered;

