#### 14.1.1.2. Relationship to Study Medication

Relationship, as indicated by the Investigator, is classed as not related/ unlikely to be related/ related (increasing severity of relationship). AEs with a missing relationship to study medication are to be regarded as related to study medication. If a subject reports the same AE more than once within that SOC/PT, the AE with the strongest relationship to study medication is to be used in the corresponding relationship summaries.

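### Once CP007 is unblinded, site blinding is stated only for subjects enrolled in CP007A, while enrolment stays open and eligibility screens only what the subject knows; a site could therefore hold a completer's allocation before that completer enters

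*Protocol*

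**What the plan says.** Protocol 5.3 deals with the period after the parent study is opened. The rule begins "In order to maintain blinding, once the CP007 study has been unblinded" and goes on: "Investigators and site staff will be kept blinded for any CP007 subjects that have enrolled into CP007A". The same section has subjects waive disclosure of their CP007 treatment and withdraws any who ask for it. It also assigns new subject numbers, with the stated aim to "ensure that all Circassia staff and Quintiles clinical staff directly involved in conduct of the study remain blind to the treatment received in CP007".

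Protocol 6.2.1 sets the entry window: "Enrolment in to the study may occur at any time after a subject has completed study CP007". It names the last CP007 follow-up visit as the ideal occasion. Table 1 in Protocol 6.1 likewise allows the enrolment visit at Visit 5 of CP007 or later.

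The eligibility safeguard is Exclusion 2 in Protocol 4.3: "Has been informed of the treatment received in study CP007".

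On safety, Protocol 6.4.1 states: "The Investigator will make a judgement regarding whether or not the AE was related to the study medication given in study CP007". SAP 14.1.1.2 tabulates that judgement: "Relationship, as indicated by the Investigator, is classed as not related/ unlikely to be related/ related".

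**The concern.** The site-level blind is tied to enrolment, and enrolment has no end date relative to the unblinding of CP007. A completer who has not yet joined when CP007 is unblinded is outside the stated protection. If the site learns that person's allocation and the person then enrols, the blind cannot be restored for that subject.

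This matters because randomisation in CP007 does not protect the comparison against selection into CP007A made with knowledge of the arm. Site staff also keep a role after entry: they ask about adverse events and attribute them to CP007 medication, and the investigator may prescribe one of the scored allergy medications.

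**Working it through.** The check is mainly a comparison of texts.

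**1. Who is protected, and from when.** Protocol 5.3 covers CP007 subjects that have enrolled into CP007A. The sentence fixes no date, so it could be meant to include people who enrol later. Even on that reading it cannot work for a subject whose allocation reached the site before enrolment.

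**2. Whether late entry is possible.** Protocol 6.2.1 leaves entry open after CP007; the final follow-up visit is only the preferred time. Exclusion 1 (immunotherapy started since completing CP007) assumes that a gap between the studies can occur. No section closes CP007A enrolment before CP007 is unblinded.

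**3. Whether another rule closes the gap.**

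| Safeguard | Whose knowledge it addresses |
|---|---|
| Exclusion 2 (Protocol 4.3) | The subject's |
| Waiver and withdrawal rule (Protocol 5.3, 8.2.2) | The subject's |
| Renumbering (Protocol 5.3) | Sponsor staff and CRO clinical staff, by its stated aim |
| Site blind (Protocol 5.3) | Investigators and site staff, for enrolled subjects |

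Protocol 5.3 also keeps CP007 numbers out of CP007A documents seen by anyone who may introduce bias. That does not help at a site enrolling its own known CP007 patients. No safeguard addresses what a site knows about a completer who has not yet enrolled.

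**4. Where such knowledge could act.**
- Entry: the investigator must be satisfied that the subject has understood the study (Protocol 6.2.1), and the subject must be willing and able to comply (inclusion criterion 3, Protocol 4.2).
- Primary endpoint: Protocol 3.2.1 leaves oral corticosteroids to the investigator's discretion, and a day with a systemic corticosteroid scores AMS = 3, the maximum. The Combined Score is TRSS/8 + AMS.
- Safety: the investigator elicits adverse events and classifies causality (Protocol 6.4.1), and the SAP tabulates the classification.

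**5. Whether the analysis would show it.** Protocol 7.4.2 undertakes to explore reasons for non-entry. SAP Section 9 starts its accounting at consent, and the sensitivity analyses in SAP 13.1.3 deal with missing diary days. Nothing flags entry relative to CP007 unblinding.

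**6. How many could be affected.** The documents give no number; the planned dates give only an indication.
- Planned end of clinical phase: June 2019. Follow-up: about 4 years per subject (Protocol synopsis).
- Latest entry that allows full follow-up: June 2019 − 4 years = about June 2015.
- Final CP007 SAP: 08 June 2016 (SAP Section 15). Assume that CP007 was not unblinded before then.
- Longest follow-up for an entrant after unblinding: June 2019 − June 2016 = about 3 years.

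The plan allows this, because Protocol 3.1 says up to 4 years. But a schedule aimed at about 4 years each implies that most entry came before unblinding. If CP007 was unblinded before its final SAP date, the window for late entry is longer.

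**7. Size.** If a share p of an arm entered this way and differed by d from the rest of that arm, the arm mean would move by p × d. The documents give neither p nor d, so no value is offered.

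The plan's only design figures are its power statements (Protocol 7.2). They reproduce from Φ(0.525/(1.29√(2/n)) − 2.241) at two-sided alpha 0.025:
- n = 266 per arm: Φ(4.693 − 2.241) = 99.3%, against at least 99% stated.
- n = 130 per arm: Φ(3.281 − 2.241) = 85.1%, against at least 80% stated.

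This point does not depend on them.

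**The case against.** The strongest reply is that the gap is one of silence and that the plan limits most of its consequences.

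- **Disclosure is not stated.** No section says that sites will receive codes for completers who have not enrolled. Protocol 8.2.2 records that CP007 already required subjects to waive unblinding, and release of CP007 codes to sites may be governed by CP007 documents that are not available here. This stands: the claim can only be that disclosure is not prevented.
- **Selective invitation.** A reader might infer that sites can choose whom to invite and could favour Cat-PAD responders. The documents do not support that. The synopsis and Protocol 3.1 say that PAC3 completers at participating sites will be invited, and the only stated limit is by country. What remains is uneven encouragement and judgement on understanding and compliance.
- **Influence on the diary.** A reader might also infer that informed staff could shape symptom reporting at visits. Protocol 6.2.3 tells subjects to complete the assessment themselves, free of staff influence, and what is completed at those visits is the monthly assessment. The primary score comes from a daily self-completed diary, kept after the Annual Visit by a subject who remains blind. The route that remains is investigator-prescribed oral corticosteroid.
- **Safety.** Questions are non-leading, events judged unrelated must still be recorded, and the analysis is descriptive. This limits the harm but does not blind the causality call.
- **Numbers.** The planned dates point to few late entrants. This also stands, although no count is given.

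**Conclusion.** The gap is real and narrow. As written, the blinding, enrolment and eligibility rules can admit a subject whose allocation the site already knows. The conclusion rests on the wording of Protocol 5.3, 6.2.1 and 4.3, and on finding no other rule in either document that covers site knowledge before enrolment.

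Its size is unknown and probably small. That expectation rests on the planned dates and on the assumption that CP007 was not unblinded before its final SAP of 08 June 2016. The documents do not support a numerical bias in the Combined Score, a statement that sites were in fact unblinded, or a statement that every late entrant's adverse events would be judged with knowledge of the arm. What remains is an avoidable route to selection at entry, to the corticosteroid component of the medication score, and to unblinded causality judgements. If no subject enrolled after site disclosure, one sentence in the report settles the matter.

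**What to change.** 1. In Protocol 5.3, extend the site-level blind to every CP007A-eligible CP007 completer at participating sites until CP007A enrolment closes. Alternatively, close CP007A enrolment before CP007 is unblinded.
2. Extend Exclusion 2 to cases where the investigator or site staff have been informed of that subject's CP007 treatment.
3. Report, by arm, how many subjects enrolled after their site had been told their allocation. Use the enrolment date, since consent may be taken earlier, at Visit 4F of CP007. If there are any such subjects, repeat the primary ANCOVA of SAP 13.1.2 without them.

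The cost is amended wording in the protocol and the unblinding plan, one count and, if needed, one further run of an existing model. Sites wait longer for some CP007 codes, and a few late entrants may be lost.
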